7.2.2 Medical Monitoring for Participant Safety

The Principal Investigator will oversee the safety of the study, including careful assessment and appropriate reporting of adverse events as outlined in Section 7.4. [name], a University of Minnesota physician and ear nose and throat specialist, will be on-site during needle electrode placement and present for any necessary medical assistance. Medical monitoring will include a regular assessment of the number and type of serious adverse events.

7.2.3 Study Stopping Rules

If during a session, the subject should show any signs of disorientation or the presence of EMG activity that cannot be stopped by the subject, the session will be stopped for that subject.

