4.4.7 Exit/Discontinuation Criteria

Subjects will exit the study if any of the following conditions exist:

- 1. Subject voluntarily withdraws from the study.
- 2. Subject death.
- 3. Subject acquires any of the listed exclusion criteria.
- 4. Subject completes the protocol.
- 5. Subject's wellbeing, in the opinion of the Investigator would be compromised by study continuation.
- 6. Subject experiences an adverse event such as seizure.
- 7. DSMB and/or IRB recommendation

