7.0 Safety and Adverse Events

7.1 Definitions

Adverse Event (AE)

An adverse event (AE) is any symptom, sign, illness or experience that develops or worsens in severity during the course of the study. Intercurrent illnesses or injuries will be regarded as adverse events. Abnormal results of laboratory or diagnostic procedures are considered to be adverse events if the abnormality:

- Results in study withdrawal
- Is associated with a serious adverse event
- Is associated with clinical signs or symptoms
- Leads to additional treatment or to further diagnostic tests
- Is considered by the Investigator to be of clinical significance.

Serious Adverse Event (SAE)

A serious adverse event (SAE) is any adverse event that is:

- Fata
- Life-threatening
- Requires or prolongs a hospital stay
- Results in persistent or significant disability or incapacity
- A congenital anomaly or birth defect

Important medical events are events that may not be immediately life-threatening, but are clearly of major clinical significance and may be SAEs.

They may jeopardize the subject, and may require intervention to prevent one or the other serious outcomes noted above.

Hospitalization

Hospitalization shall include any initial admission (even if less than 24 hours) to a healthcare facility as a result of a precipitating clinical adverse effect; to include transfer within the hospital to an intensive care unit. Hospitalization or prolongation of hospitalization in the absence of a precipitating, clinical adverse effect (e.g., for a preexisting condition not associated with a new adverse effect or with a worsening of the preexisting condition; admission for a protocol-specified procedure) is not, in itself, a serious adverse effect.

Unanticipated Adverse Device Effect (UADE)

An unanticipated adverse device effect is any serious adverse effect on health or safety or any life-threatening problem or death caused by, or associated with, a device, if that effect problem, or death was not previously identified in nature, severity, or degree of incidence in the investigational plan, or any other unanticipated serious problem associated with a device that relates to the rights, safety, or welfare of subjects.

Unanticipated Problems Involving Risk To Subjects or Others (UPIRTSO)

An adverse event that in the opinion of the Principal Investigator is unexpected, related to the device, and serious.

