7.2.1 Anticipated Risks / Risk Mitigation

- 1. Personal information: There is a small risk of loss of confidentiality. Subjects will be asked if they have any medical conditions and if they are taking any medications. This is important to know so that only those subjects who meet the inclusion and exclusion criteria are accepted into the study. A number of procedures are in place to protect participant confidentiality. Every participant enrolled in the study will receive a unique code number. All records and results will be labeled with this code number and the code will be shared only with the study investigators. Any information that is included in published manuscripts (e.g. demographic information) will not be linked to any other information that would identify who the subject was.
- 2. TMS: Risks associated with TMS are rare but should be recognized and prevented with appropriate precautions. Serious adverse risks include the induction of a seizure. There have been reports of a seizure and induced mania from rTMS but none of these side effects have been reported with the type of rTMS that we are doing in this study. Mild adverse effects include fainting, headache, dental pain, and other changes in memory, mood, and hearing. The overall occurrence of a mild adverse event is 5% in sham and real TMS sessions combined (Maizey et al., 2013). Participants will be asked to complete the form "Subject Report of Symptoms" before TMS testing and at the end of the experiment so that the required actions are taken in case there are any changes to their health status. Participants will be instructed to contact study staff if they noticed any of the symptoms listed above after participation in the study. In addition, study staff may contact participants (via email or phone call) to follow-up on any issues or symptoms that occur during the experiment. People with a history of seizure within the last two years or a history of bipolar disorder will not be allowed to participate in this study. The tests may be discontinued without the participant's consent if the study team observes any abnormal responses. TMS delivery may also interfere with implanted devices and, thus, TMS is not appropriate for persons with medical devices such as deep brain stimulators, pace makers and medication pumps. Currently, the effects of TMS on hormonal cycles and the unborn fetus are unknown.

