7.3 Anticipated Adverse Events

Risks associated with TMS are rare but should be recognized and prevented with appropriate precautions. Serious adverse risks include the induction of a seizure. Mild adverse effects include fainting, headache, dental pain, and other changes in memory, mood, and hearing. TMS delivery may also interfere with implanted devices.

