7.4.2 Serious Adverse Events

Principal investigation contact information for Serious Adverse Event Notification:

[name]

[name] (Telephone)

At the time of the initial report, the following information will be provided:

Study Identifier
 Study Center
 Whether study treatment was discontinued
 Reason the event is classified as serious

- Subject Number - Event Description

- Date of Onset - Investigator assessment of association

- Current Status between event and study device

Serious Adverse Events that are at least possibly related must be reported to the IRB within 10 working days, and to FDA within 15 calendar days.

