7.4.3 Unanticipated Adverse Device Effects

We will submit a completed Form FDA 3500 A to the FDA's Center for Devices and Radiological Health for any observed or volunteered adverse effect that is determined to be an unanticipated adverse device effect. A copy of this completed form will be provided to all participating sub-investigators.

The completed Form FDA 3500 A will be submitted to the FDA as soon as possible and, in no event, later than 10 working days after the Sponsor-Investigator first receives notice of the adverse effect.

If the results of our follow-up evaluation show that an adverse effect that was initially determined to not constitute an unanticipated adverse device effect does, in fact, meet the requirements for reporting; we will submit a completed Form FDA 3500 A as soon as possible, but in no event later than 10 working days, after the determination was made.

For each submitted Form FDA 3500 A, we will identify all previously submitted reports that that addressed a similar adverse effect experience and we will provide an analysis of the significance of newly reported adverse effect in light of the previous, similar report(s).

We will report to the IRB any observed or volunteered adverse effect that is determined to meet all of the following criteria:

- 1) associated with the investigational device or, if applicable, other study treatment or diagnostic product(s);
- 2) a serious adverse effect; and
- 3) an unexpected adverse effect.

Applicable adverse effects will be reported to the IRB as soon as possible and, in no event, later than 10 calendar days following the Sponsor-Investigator's receipt of the respective information.

Adverse effects which are

- 1) associated with the investigational drug or, if applicable, other study treatment or diagnostic product(s);
- 2) fatal or life-threatening; and
- 3) unexpected

will be reported to the IRB within 24 hours of receipt of the respective information.

If the Adverse Event is Serious, Unanticipated, Device Related, and determined by the Sponsor to present an unreasonable risk to subjects, the Sponsor must terminate the study within 5 working days of that determination.

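### Section 7.2.3, Study Stopping Rules, stops only one subject's session; no visible clause pauses rTMS in other participants after a seizure or an anticipated related SAE

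*Combined protocol and SAP*

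**What the plan says.** These clauses in the combined protocol and SAP bear on stopping:

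- **7.2.3 Study Stopping Rules.** One sentence. If a subject becomes disoriented or shows EMG activity that the subject cannot stop, "the session will be stopped for that subject".
- **4.4.7 Exit/Discontinuation Criteria.** Item 6 exits a subject on this condition: "Subject experiences an adverse event such as seizure". Item 5 lets the investigator exit a subject whose wellbeing is at stake. Item 7 lists a DSMB or IRB recommendation, although 7.5 provides no board.
- **7.4.2 Serious Adverse Events.** These "must be reported to the IRB within 10 working days, and to FDA within 15 calendar days" when a causal link is at least possible.
- **7.4.3 Unanticipated Adverse Device Effects.** Termination within 5 working days is required under this condition: "If the Adverse Event is Serious, Unanticipated, Device Related, and determined by the Sponsor to present an unreasonable risk to subjects". Unexpected, associated events that are fatal or life-threatening "will be reported to the IRB within 24 hours of receipt of the respective information".
- **7.3 Anticipated Adverse Events.** "Serious adverse risks include the induction of a seizure".
- **7.2.1 Anticipated Risks.** On seizure and mania: "none of these side effects have been reported with the type of rTMS that we are doing in this study".
- **7.1 Definitions.** A UADE is an effect that "was not previously identified in nature, severity, or degree of incidence in the investigational plan".

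Sections 7.2, 7.2.2 and 7.4 add continuous monitoring, investigator oversight with regular SAE assessment, and prompt review of events. Section 4.2 allows for early termination.

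**The concern.** A section with this title should say when stimulation stops across the study. This one says when it stops for one person on the day. A seizure is the serious risk that the protocol itself names, yet the visible text does not say what happens to the next booked participant.

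This is a patient-safety matter. Aim 1 is safety, and its hypothesis is zero SAEs with full completion. Section 2.1 says that, to the team's knowledge, nobody has yet modulated laryngeal motor cortex excitability in either population. Section 4.4.1 expects no direct benefit from taking part, and half of the planned sample are healthy controls. Whether such a person is stimulated before the IRB hears of a seizure is left to the investigator's discretion.

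**Working it through.** **Step 1: does any clause hold the other participants?** The protocol gives no stopping boundary or derived figure to reproduce, so this step compares the clauses.

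| Section | Acts on | Pause for others? |
|---|---|---|
| 7.2.3 | one subject's session | no |
| 4.4.7 item 6 | the affected subject | no |
| 4.4.7 items 5 and 7 | subjects, by judgement or recommendation | not automatic |
| 7.2, 7.2.1 | the individual showing the response | no |
| 7.4.2 | reporting only | no |
| 7.4.3 termination | the whole study | only after a Sponsor finding |
| 7.2.2, 7.4, 4.2 | oversight, review, possible termination | discretionary |

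**Step 2: does the 7.4.3 termination clause cover a seizure?** Not clearly. Section 7.3 lists seizure as anticipated. On the other hand, 7.2.1 says none has been reported with this type of rTMS, and the UADE definition in 7.1 includes degree of incidence, so a seizure could be argued to be unanticipated. Even on that reading, the clause waits for a finding of unreasonable risk and sets no hold before it.

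Classification may also matter. Section 7.1 says that important medical events may be SAEs, so a brief seizure without admission might not be classed as one. Under 7.4.1, events that are neither SAEs nor UADEs reach the IRB with the continuing review report.

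**Step 3: how many sessions fall before the deadlines?** Inputs: 40 planned participants (4.4.1), one session each (4.1), and 24 months from enrolment to final report (4.2). Assumption: even accrual over 12 to 24 months, where 24 is an outer limit because it includes the final report.

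Sessions in a window = 40 ÷ accrual days × window days. Ten working days are taken as 14 calendar days.

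- 24 months: 40 ÷ 730.5 = 0.0548 per day, or one session per 18.3 days.
- 12 months: 40 ÷ 365.25 = 0.1095 per day, or one session per 9.1 days.

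| Window | 24 months | 12 months |
|---|---|---|
| 1 day (7.4.3, fatal or life-threatening, unexpected) | 0.05 | 0.11 |
| 10 calendar days (7.4.3, IRB, if read as a UADE) | 0.55 | 1.10 |
| 14 days (7.4.2, IRB) | 0.77 | 1.53 |
| 15 days (7.4.2, FDA) | 0.82 | 1.64 |

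With the 50 participants that 4.4.1 allows for recruitment, the 7.4.2 rows become 0.96 to 1.92 (IRB) and 1.03 to 2.05 (FDA). These are latest dates, so faster reporting lowers the exposure.

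**Step 4: how likely is a seizure to trigger the rule?** The documents give no seizure rate. With assumed per-participant risk p, the chance of at least one in 40 is 1 − (1 − p)^40:

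- p = 0.01%: 0.4%
- p = 0.1%: 3.9%
- p = 1%: 33%

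**Step 5: what would be known at that moment?** One seizure among the first 20 participants gives an exact (Clopper–Pearson) 95% interval of 0.1% to 24.9%. This does not measure the effect of the missing clause. It shows how little the data could say about whether to resume.

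**The case against.** The strongest reply is that the plan is more than the visible text. Section 4.4.4 says the seizure risk needs a rigorous safety plan, gives an acute response with oxygen and lorazepam, and points to an attached TMS safety white paper. Section 4.4.6 points to Section 3 of the IRB protocol, and Section 14 lists FDA rTMS guidelines and an experiment checklist. Any of these might contain a pause rule. That stands, and it limits the finding to the visible text.

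The second reply is that the risk is low and a pause would happen anyway. By the protocol's own account in 4.4.4 and 5.3, stimulation is low-rate and sub-threshold, within safety guidelines, and used by the laboratory without incident. Visits take place in clinical research units with emergency cover (7.2). In a small study run by one team, those who would order a pause are those running the session. This too has weight, although the reassurance concerns dose rather than the new target, and discretion held by a Sponsor-Investigator is not independent of study conduct.

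Third, the expected benefit is tiny. Chance of a first seizure × about 1.53 further sessions × risk gives 0.0392 × 1.53 × 0.001 ≈ 0.00006 further seizures at 0.1% risk, and 0.331 × 1.53 × 0.01 ≈ 0.005 at 1%. The arithmetic is right if risk stays fixed, but a first seizure may be the sign that risk is higher than assumed.

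Finally, Step 4 covers seizure only, while the proposed trigger also includes electrode-related SAEs. Section 7.2.1 supports including them, since it names haemorrhage, infection and dysphagia, but their frequency has not been estimated here. Requiring IRB agreement to resume is also one option among several.

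**Conclusion.** The concern holds. No visible clause pauses rTMS in other participants after a seizure or an anticipated related SAE. The protocol does have a study-level termination clause in 7.4.3, but it does not clearly cover a seizure and sets no interim hold.

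The size is modest: about 0.8 to 1.6 further sessions before the 7.4.2 deadlines with 40 participants, and up to about 2 with 50. This rests on assumed even accrual over 12 to 24 months. How often the rule would be needed depends on a seizure risk that the documents do not give. It is an inexpensive improvement worth considering, with medium confidence because the attachments could not be seen.

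**What to change.** Leave the existing sentence in 7.2.3 as it is and add:

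> After any seizure, or any SAE at least possibly related to TMS, rTMS or electrode placement, whether or not anticipated, enrolment and rTMS sessions pause until the investigator and the IRB have reviewed the event and the IRB has agreed to resumption.

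Naming any seizure as a trigger removes the dependence on how the event is classified. If an attachment already contains such a rule, cite it in 7.2.3 instead.

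The cost is one sentence, with no added visits, tests or participants. A delay arises only if a triggering event occurs. The documents do not give the IRB's review time. If it is 2 to 8 weeks (assumption), the sessions deferred, not lost, run from 0.0548 × 14 = 0.8 to 0.1095 × 56 = 6.1.

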7.3 Anticipated Adverse Events

Risks associated with TMS are rare but should be recognized and prevented with appropriate precautions. Serious adverse risks include the induction of a seizure. Mild adverse effects include fainting, headache, dental pain, and other changes in memory, mood, and hearing. TMS delivery may also interfere with implanted devices.

7.4 Adverse Event Reporting

All Adverse Events occurring during the study period must be recorded. The clinical course of each event will be followed until resolution, stabilization, or until it has been determined that study treatment or participation is not the cause.

We will promptly review documented adverse effects and abnormal test findings to determine

- 1) if the abnormal test finding should be classified as an adverse effect;
- 2) if there is a reasonable possibility that the adverse effect was caused by the investigational device or, if applicable, other study treatment or diagnostic product(s); and
- 3) if the adverse effect meets the criteria for a serious adverse effect.

If our final determination of causality is "unknown and of questionable relationship to the investigational device or, if applicable, other study treatment or diagnostic product(s)", the adverse effect will be classified as associated with the use of the investigational device or study treatment or diagnostic drug product(s) for reporting purposes. If our final determination of causality is "unknown but not related to the investigational device or, if applicable, other study treatment or diagnostic product(s)", this determination and the rationale for the determination will be documented in the respective subject's case history.

7.4.1 Adverse Events:

All observed or volunteered adverse effects and abnormal test findings, regardless of treatment group, if applicable, or suspected causal relationship to the investigational device or, if applicable, other study treatment or diagnostic product(s) will be recorded in the subjects' case histories. For all adverse effects, sufficient information will be pursued and/or obtained so as to permit:

- 1) an adequate determination of the outcome of the effect (i.e., whether the effect should be classified as a serious adverse effect) and;
- 2) an assessment of the casual relationship between the adverse effect and the investigational device or, if applicable, the other study treatment or diagnostic product(s).

Adverse effects or abnormal test findings felt to be associated with the investigational device or, if applicable, other study treatment or diagnostic product(s) will be followed until the effect (or its sequelae) or the abnormal test finding resolves or stabilizes at a level acceptable to the Sponsor-Investigator.

Adverse Events that do not qualify as Serious Adverse Events, or as Unanticipated Adverse Device Effects will be reported the IRB with the continuing review progress report. These events will be reported to FDA with the IDE Annual Report.

7.4.2 Serious Adverse Events

Principal investigation contact information for Serious Adverse Event Notification:

[name]

[name] (Telephone)

At the time of the initial report, the following information will be provided:

Study Identifier
 Study Center
 Whether study treatment was discontinued
 Reason the event is classified as serious

- Subject Number - Event Description

- Date of Onset - Investigator assessment of association

- Current Status between event and study device

Serious Adverse Events that are at least possibly related must be reported to the IRB within 10 working days, and to FDA within 15 calendar days.

7.4.3 Unanticipated Adverse Device Effects

We will submit a completed Form FDA 3500 A to the FDA's Center for Devices and Radiological Health for any observed or volunteered adverse effect that is determined to be an unanticipated adverse device effect. A copy of this completed form will be provided to all participating sub-investigators.

The completed Form FDA 3500 A will be submitted to the FDA as soon as possible and, in no event, later than 10 working days after the Sponsor-Investigator first receives notice of the adverse effect.

If the results of our follow-up evaluation show that an adverse effect that was initially determined to not constitute an unanticipated adverse device effect does, in fact, meet the requirements for reporting; we will submit a completed Form FDA 3500 A as soon as possible, but in no event later than 10 working days, after the determination was made.

For each submitted Form FDA 3500 A, we will identify all previously submitted reports that that addressed a similar adverse effect experience and we will provide an analysis of the significance of newly reported adverse effect in light of the previous, similar report(s).

We will report to the IRB any observed or volunteered adverse effect that is determined to meet all of the following criteria:

- 1) associated with the investigational device or, if applicable, other study treatment or diagnostic product(s);
- 2) a serious adverse effect; and
- 3) an unexpected adverse effect.

Applicable adverse effects will be reported to the IRB as soon as possible and, in no event, later than 10 calendar days following the Sponsor-Investigator's receipt of the respective information.

Adverse effects which are

- 1) associated with the investigational drug or, if applicable, other study treatment or diagnostic product(s);
- 2) fatal or life-threatening; and
- 3) unexpected

will be reported to the IRB within 24 hours of receipt of the respective information.

If the Adverse Event is Serious, Unanticipated, Device Related, and determined by the Sponsor to present an unreasonable risk to subjects, the Sponsor must terminate the study within 5 working days of that determination.

